### 15.3. Assessment for restaging

after III\* course and at EOI:

- Measurable lesion assessment on CT scan of neck, chest, abdomen and pelvis, to be performed with and without contrast;
- FDG-PET scan (mandatory);
- Bone marrow biopsy only if positive at baseline.

Patients who achieve a response less than stable disease after first restaging or at EOI are considered out of treatment and will be shifted to survival follow up

\*Within 7 days before cycle IV day 1

**Clinical and Laboratory CMV infections monitoring:** Every two weeks starting from C1D1.

**Prophylaxis for PJP:** all patients will receive PJP prophylaxis during idelalisib treatment and for 2 to 6 months after stopping treatment; patients have to be monitored for respiratory signs and symptoms.

#### **15.4. EOT phase**

at 4-6 weeks after last treatment administration

- Physical Examination;
- ECOG;
- Vital Signs;
- Hematology including Hemoglobin, Platelets, White blood cell count (WBC) with differential;
- Blood chemistry including creatinine, total bilirubin, LDH, AST, ALT, serum proteins with electrophoresis, immunoglobulin levels;
- Pregnancy test (if applicable);
- Electrocardiogram;
- LVEF by either bi-dimensional echocardiogram or cardiac scintigraphy (MUGA);
- Measurable lesion assessment on CT scan of neck, chest, abdomen and pelvis, to be performed with and without contrast (unless the subject already has had per-protocol assessments  $\leq 4$  weeks prior);
- FDG-PET scan (mandatory) unless the subject already has had per-protocol scan  $\leq 4$  weeks prior;
- Bone marrow biopsy only if positive at baseline;
- Molecular evaluation of BCL-2 rearrangement on marrow blood only if positive at baseline;
- Drug accountability
- AEs assessment
- Recording of concomitant medications.

Subjects lost to follow up should be recorded as such on the eCRF. All subjects who discontinue study treatment, including those who refuse to return for a final visit, should be contacted for a list of antineoplastic therapies received after discontinuation of study treatment.

#### **15.5. Maintenance period**

every 3 months for the first year and every 4 months for the second year

Maintenance phase begins after the end of induction and continues until 2 years or PD documentation or unacceptable toxicity, whichever comes first only for patients who achieve at least PR at EOT.

- Physical Examination;
- ECOG;
- Vital Signs;
- Clinical Laboratory Evaluations;
- CT scan of neck, chest, abdomen and pelvis, to be performed with and without contrast (counting months with a  $\pm 7$  days range from EOT imaging evaluation);

- FDG-PET scans during maintenance are optional and will be performed at clinician discretion only if in accordance to the site clinical practice.

### **15.6. Follow up period**

(every 6 months)

- For patients in SD at the EOI restaging (ie for patients who not continue with maintenance phase).
- For patients in SD, PR or CR at the end of maintenance phase.

The follow up phase continues until 2 years, PD or a new anti-lymphoma therapy, whichever comes first. If any of the above occurs, patients will enter the survival follow up period till the completion of two years globally.

- Physical Examination;
- ECOG;
- Vital Signs;
- Pregnancy test (if applicable);
- Clinical Laboratory Evaluations;
- FDG-PET and CT scan of neck, chest, abdomen and pelvis, to be performed with and without contrast (counting months with a  $\pm 7$  days range from EOT imaging evaluation);
- FDG-PET scans during follow-up are optional and will be performed at clinician discretion only if in accordance to the site clinical practice.

### **15.7. Survival Follow up**

For patients in PD or for patients who start a new anti-lymphoma treatment. Every 3 months until 2 years (counting follow up phase too if applicable) or until study closure whichever comes first. Survival follow up can be performed with a telephone contact too and the investigator must report: disease status, patients' status (dead or alive and date of death, new anti-lymphoma therapy).

### **15.8. Early withdrawn (EW)**

discontinuation from study treatment

- Physical Examination;
- ECOG;
- Vital Signs;
- Hematology including Hemoglobin, Platelets, White blood cell count (WBC) with differential;
- Blood chemistry including creatinine, total bilirubin, LDH, AST, ALT, serum proteins with electrophoresis, immunoglobulin levels;
- Pregnancy test (if applicable);
- Electrocardiograms;
- LVEF by either bi-dimensional echocardiogram or cardiac scintigraphy (MUGA);
- Measurable lesion assessment on CT scan of neck, chest, abdomen and pelvis, to be performed with and without contrast unless the subject already has had per-protocol scan  $\leq 4$  weeks prior;
- FDG-PET scan (mandatory) unless the subject already has had per-protocol scan  $\leq 4$  weeks prior;
- Drug accountability
- AEs assessment
- Recording of concomitant medications.

## 15.9. Schedule of assessments

	Screening	Treatment (Induction)						Restaging after 3 cycles, EOI, EOT, EW	Maintenance g	FU e	OS- FU
		Cycle 1			Cycle 2-6						
		-28 to D1	D1	D8	D15	D1	D8				
Informed consent	X										
Inclusion/Exclusion	X										
Medical History	X										
Height	X										
Weight	X	X	X	X	X						
Physical exam	X	X	X	X	X		X	X	X		
Pregnancy test	X	X	X	X	X		X	X	X		
Vital signs	X	X	X	X	X		X	X	X		
ECOG	X	X	X	X	X		X	X	X		
Hematology	X	X	X	X	X		X	X	X		
Chemistry	X	X	X	X	X		X	X	X		
Virology	X										
12-lead ECG	X						X h				
Tumor biopsy b	X										
CT of neck, chest, abdomen, pelvis	X						X f	X f	X f		
FDG-PET	X						X f	X f	X f		
LVEF measurement	X						X h				
BM biopsy	X						X a	X a	X a		
BCL-2 rearrangement	X						X ah				
B symptoms	X	X	X	X	X		X	X	X		
Idelalisib		BID									
Obinutuzumab		X	X	X	X			X g			
CMV monitoring c	X			X	X		X				

	Screening	Treatment (Induction)						Restaging after 3 cycles, EOI, EOT, EW	Maintenance g	FU e	OS- FU	
		Cycle 1			Cycle 2-6							
	-28 to D1	D1	D8	D15	D1	D8	D15					
PJP prophylaxis d		X	X	X	X	X	X	X				
Survival follow up contact											X	
Concomitant medications	Recorded from screening through 30 days after the last dose of treatment.											
Adverse event reporting		Recorded from first dose of study drug through 30 days after the last dose of treatment.										
Serious adverse event	Reported from signing of the informed consent from through last patient last visit											

a only if positive at baseline/previous assessment;

b Histological centralized review is compulsory for treatment start, but the local pathology report is sufficient for patient enrollment;

c Every two weeks starting from C1D1;

d All patients will receive prophylaxis for PJP during idelalisib treatment and for 2 to 6 months after stopping treatment; patients have to be monitored for respiratory signs and symptoms;

e Every 6 months for 2 years only for CR, PR or SD patients at the end of treatment until PD, unacceptable toxicity or a new anti-lymphoma therapy;

f FDG-PET scan is mandatory at baseline, after induction cycle 3, at the EOI, at the end of treatment after 2 years of maintenance or in case of early withdrawal (EOT) and at relapse/progression, unless the subject already has had per-protocol scan ≤4 weeks prior; all additional PET scans (every 3 months during the first year of maintenance, every 4 months during the second year of maintenance and during follow-up) are optional and will be done at clinician discretion only if in accordance to the site clinical practice;

g obinutuzumab on day 1 every two months, procedures every 3 months for first year and every 4 months for the second year;

h only EOI and EOT.

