### **Maintenance**

For patients achieving at least a partial response at the end of induction, a maintenance phase with obinutuzumab is scheduled (on day 1 every two months for two years or until progression or unacceptable toxicity, whichever comes first)

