### **13.4.2. Obinutuzumab**

All obinutuzumab infusions should be administered after premedication with oral acetaminophen and an antihistamine. The prophylactic use of corticosteroids (e.g., 100 mg of IV prednisolone or equivalent) may also be considered for patients thought to be at high risk for infusion-related reactions (IRRs), if deemed appropriate by the investigator, and should be administered prior to the obinutuzumab infusion. On Cycle 1 Day 1, it is recommended that oral prednisone, prednisolone, or methylprednisolone be given within 12 hours as a premedication but at least 60 minutes prior to the obinutuzumab infusion.

Premedication with prednisone or prednisolone is mandatory in patients who had an IRR and should continue until IRRs no longer occur during antibody infusion.

If it is the strong preference of the investigator or of the site (e.g., for logistical reasons) or if the patient is at increased risk for an IRR (high tumor burden, high peripheral lymphocyte count), the administration of obinutuzumab infusion can be split over 2 days. In all parts of the study, obinutuzumab must be administered in a clinical (inpatient or outpatient) setting. Full emergency resuscitation facilities should be immediately available, and patients should be under the close supervision of the investigator at all times.

The commonly experienced IRRs have been characterized by fever, chills, flushing, nausea, vomiting, hypotension, hypertension, fatigue, and other symptoms.

Respiratory infusion-related symptoms, such as hypoxia, dyspnea, bronchospasm, larynx and throat irritation, and laryngeal edema, have also been reported. These IRRs were mostly mild or moderate (NCI CTCAE v. 5.0, Grade 1 and 2 events), and < 10% of the events were severe (Grade 3 events), occurring predominantly during the first hour of the infusion or shortly after the first infusion had finished. The events resolved with the slowing or interruption of the infusion and supportive care. The incidence and severity of IRRs decreased with subsequent infusions. Extensive tumor burden predominantly localized in the blood circulation may be a predisposing factor for the development of IRRs.

IRRs may be clinically indistinguishable from IgE-mediated allergic or anaphylactic reactions.

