## **13.5. Prophylactic measures**

### **Prevention of infections**

Fatal and/or serious infections occurred in patients treated with idelalisib monotherapy or in combination with rituximab or with unapproved combination therapies. The most common infections were pneumonia, sepsis, and febrile neutropenia. Treatment with idelalisib should not be initiated in patients with any evidence of ongoing systemic bacterial, fungal, or viral infection. Treat infections prior to initiation of idelalisib therapy.

On the basis of its anticipated mode of action, resulting in profound B-cell depletion, obinutuzumab may be associated with an increased risk of infections. Infections have been reported in patients receiving obinutuzumab. Therefore, obinutuzumab should not be administered to patients with active severe infections.

Serious or fatal *Pneumocystis jirovecii* pneumonia (PJP) or cytomegalovirus (CMV) occurred in <1% of patients treated with idelalisib. Provide PJP prophylaxis during treatment with idelalisib. Regular clinical and laboratory monitoring for CMV infection is recommended in patients with history of CMV infection or positive CMV serology at the start of treatment with idelalisib.

Treatment-emergent Grade 3 or 4 neutropenia occurred in patients treated with idelalisib monotherapy or in combination with rituximab or with unapproved combination therapies.

Grade 3 or 4 neutropenia, including febrile neutropenia, have been reported with obinutuzumab administration.

In case of Grade 3 or 4 neutropenia blood counts should be monitored at least every 2 weeks for the first 6 months of therapy, and at least weekly in patients while neutrophil counts are less than 1.0, until neutrophil values return to at least Grade 2.

Use of G-CSF has been found to result in a rapid normalization of neutrophils, similar to what has been observed in patients treated with rituximab. The use of G-CSF is allowed for treatment of neutropenia in this study. Primary prophylaxis with G-CSF is recommended according to the American Society of Clinical Oncology (ASCO) [29], European Organisation for Research and Treatment of Cancer (EORTC) [30], and European Society for Medical Oncology (ESMO) [31] guidelines, namely for patients who are  $\geq 60$  years old and/or with comorbidities.

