### **Thrombocytopenia**

Severe and life-threatening thrombocytopenia, including acute thrombocytopenia (occurring within 24 hours after the infusion), has been observed during treatment with obinutuzumab. Fatal hemorrhagic events have also been reported in patients treated with obinutuzumab. It seems that the first cycle is the greatest risk of hemorrhage in patients treated with obinutuzumab. A clear relationship between thrombocytopenia and hemorrhagic events has not been established. Patients should be closely monitored for thrombocytopenia, especially during the first cycle; regular laboratory tests should be performed until the event resolves, and dose delays should be considered in case of severe or life-threatening thrombocytopenia. Transfusion of blood products (i.e., platelet transfusion) according to institutional practice is at the discretion of the treating physician.

Patients treated with concomitant medication, which could possibly worsen thrombocytopenia-related events (e.g., platelet inhibitors and anticoagulants), may be at greater risk of bleeding when the platelet count is  $< 20,000/\mu\text{L}$ . When possible, replace prior therapy with Vitamin K antagonists, such as warfarin, with low-molecular weight heparin (LMWH) or new oral anticoagulants (NOACs) before Cycle 1 Day 1.

Clinical decision making may be adjusted depending on the patient-specific assessment of benefit and risk.

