### **Obinutuzumab**

There will be no obinutuzumab dose modification in this study. Consider treatment interruption if patients experience an infection, Grade 3 or 4 cytopenia, or a  $\geq$  Grade 2 non-hematologic toxicity. Any NCI CTCAE (v. 5.0) toxicity Grade  $\geq 3$  in severity that is deemed related to obinutuzumab treatment will require interruption of study treatment until resolution to Grade  $\leq 2$  or  $\geq 80\%$  of baseline, whichever is lower.

Resumption of obinutuzumab treatment may be considered in patients with resolution of toxicities to Grade  $\leq 1$  within 2 weeks at the discretion of the investigator, after consultation with the Medical Monitor. Failure of such toxicities to resolve after 2-week delay in study treatment will require permanent discontinuation of obinutuzumab.

Continuation of study treatment following dose delays beyond 2 weeks will require consultation with and approval of the Medical Monitor based on an assessment of the benefit-risk analysis of continuing to delay study treatment.

Patients in whom toxicities have not resolved (i.e., to Grade  $\leq 1$  or  $\geq 80\%$  of baseline) may have their study treatment delayed by up to 2 weeks. If all study drug-related toxicities have resolved to Grade  $\leq 1$  or  $\geq 80\%$  of baseline, the patient may resume idelalisib and obinutuzumab dosing on the regular every-28-day schedule.

Patients who do not fulfill the criteria for dosing after the additional 2 weeks have elapsed may be discontinued from study treatment and be followed for safety outcomes. Exceptions on the basis of ongoing clinical benefit may be allowed following a careful assessment and discussion of risk versus benefit with the patient by the investigator and approval from the Medical Monitor. In addition, delay of therapy because of toxicities not attributed to study drug may not require discontinuation and will be discussed with the Medical Monitor.

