### 15.2. Treatment period (Induction)

Before each course of chemotherapy (within 24 hours prior to Day 1):

- Physical Examination, including weight;
- ECOG;
- Vital Signs;
- B-symptoms;
- Hematology including Hemoglobin, Platelets, White blood cell count (WBC) with differential;
- Blood chemistry including creatinine, total bilirubin, LDH, AST, ALT, serum proteins with electrophoresis, immunoglobulin levels;
- AE assessment;
- Pregnancy test (if applicable);
- Concomitant medications.

At days 8 and 15 during the first cycle:

- Vital Signs;
- Hematology including Hemoglobin, Platelets, White blood cell count (WBC) and neutrophils;
- Blood chemistry including creatinine, total bilirubin, LDH, AST, ALT;
- AE assessment

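### No hematology or chemistry is scheduled before each two-monthly maintenance infusion of obinutuzumab; on a common start date, 7 of 12 infusions have no scheduled blood test in the same month

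*Combined protocol and SAP*

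**What the plan says.** Section 13.3 gives responders maintenance obinutuzumab "on day 1 every two months for two years or until progression or unacceptable toxicity". Section 15.5 places the maintenance procedures, including clinical laboratory evaluations and CT, "every 3 months for the first year and every 4 months for the second year". The maintenance column of the table in 15.9 lists hematology and chemistry as separate rows, and footnote g to that column states both calendars together: "obinutuzumab on day 1 every two months, procedures every 3 months for first year and every 4 months for the second year".

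Induction is handled differently. Section 15.2 ties hematology and chemistry to dosing: "Before each course of chemotherapy (within 24 hours prior to Day 1").

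Section 13.12 makes obinutuzumab dosing depend partly on laboratory results: "Consider treatment interruption if patients experience an infection, Grade 3 or 4 cytopenia". It also requires interruption for any toxicity of grade 3 or higher judged related to obinutuzumab.

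**The concern.** The two calendars do not line up. A site that follows the schedule exactly will give some maintenance infusions with no recent blood count or liver test. The interruption rules in 13.12 work only if the abnormality is known, and an asymptomatic cytopenia or transaminase elevation is found only by testing. The protocol itself warns in 13.12 that neutropenia on obinutuzumab can be severe, prolonged or of late onset. What is at stake is a dose given that the protocol's own rules might have held, and some laboratory toxicity that is never recorded.

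**Working it through.** The protocol states no count of covered infusions, so there is no figure to reproduce. The check is a calendar count.

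**Inputs**
- Infusions every 2 months for 2 years (13.3): 24 / 2 = 12, taken at months 2, 4, ..., 24.
- Blood tests every 3 months in year 1 and every 4 months in year 2 (15.5; 15.9 footnote g): months 3, 6, 9, 12, 16, 20 and 24. The end-of-induction (EOI) visit, where the 15.9 table also lists hematology and chemistry, is month 0.
- Assumption: both calendars start at EOI. The protocol does not date the first maintenance infusion relative to EOI.
- One month = 730.5 / 24 = 30.4 days.

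**Rule.** Age of the last scheduled result = infusion date minus the latest visit on or before it. An infusion is covered if that age is within the look-back allowed.

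**Common start, nominal dates**

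| Infusion month | Last scheduled test (month) | Age |
|---|---|---|
| 2 | 0 | 2 months |
| 4 | 3 | 1 month |
| 6 | 6 | 0 |
| 8 | 6 | 2 months |
| 10 | 9 | 1 month |
| 12 | 12 | 0 |
| 14 | 12 | 2 months |
| 16 | 16 | 0 |
| 18 | 16 | 2 months |
| 20 | 20 | 0 |
| 22 | 20 | 2 months |
| 24 | 24 | 0 |

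- No test in the same month: months 2, 4, 8, 10, 14, 18, 22, so 7 of 12 (58%).
- No test within the preceding month (31-day look-back): months 2, 8, 14, 18, 22, so 5 of 12 (42%).
- Infusions at months 0, 2, ..., 22, with EOI covering month 0, give the same 7 and 5.

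**Sensitivity to the visit window.** Section 15.5 allows maintenance CT to move by 7 days either way. If the blood tests move with the CT (an assumption), a month-3 visit done 7 days late falls 30.4 - 7 = 23.4 days before the month-4 infusion; the same holds for months 9 and 10. A 28-day look-back then leaves 5 of 12 uncovered. On nominal dates those two gaps are 30.4 days, and a 28-day look-back leaves 7 of 12. A look-back of 21 days or less leaves 7 of 12 even at the favourable edge of the window.

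**Sensitivity to the start date.** With infusions at months 1, 3, ..., 23 and nominal visits, only months 3 and 9 coincide with a test, so 10 of 12 have no same-month test; a 31-day look-back leaves 5 of 12 (months 5, 11, 15, 19, 23). The last scheduled result is then 3 months old at months 15, 19 and 23 (15 - 12, 19 - 16, 23 - 20).

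**Extra samples if tests are added.** The 7 visit dates and 12 infusion dates share months 6, 12, 16, 20 and 24, giving 7 + 12 - 5 = 14 distinct sampling dates, or 7 more than now.

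**The case against.** The strongest reply is that a schedule sets minimum research procedures, and that other text and ordinary practice supply the rest.

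- **Synopsis, assessments schedule.** Bloods are collected before each cycle. Cycles are the six 28-day induction cycles, and 15.5 and footnote g are specific to maintenance, so this does not reach maintenance infusions.
- **Section 13.5, tumor lysis prophylaxis.** The text on later infusions presupposes a lymphocyte count, but only in patients still at risk of tumor lysis.
- **Sections 13.5 and 13.12, cytopenias.** The neutropenia rule that "blood counts should be monitored at least every 2 weeks for the first 6 months of therapy" applies once grade 3 or 4 neutropenia is known, and the first 6 months is about the length of induction. For platelets, "Patients should be closely monitored for thrombocytopenia, especially during the first cycle; regular laboratory tests should be performed until the event resolves"; this sets no maintenance timepoint. The resumption criteria in 13.12 also act on toxicity already identified.
- **Section 20.2.** Investigators may do tests needed for medical care. That permits a pre-dose count; it does not require one.
- **Section 18.** The DSMB reviews safety about every 3 months, but cannot review a count that was not taken.

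Part of the reply stands. A reader might infer that patients receive these infusions with no clinical check at all. The documents do not support that. Section 13.4.2 says that "obinutuzumab must be administered in a clinical (inpatient or outpatient) setting", under close supervision by the investigator. The infusion table in 13.2.2 sets each rate by how the previous infusion was tolerated, and the infusion-reaction text in 13.12 deals with blood pressure around each infusion. Sections 15.9 and 16.3 record adverse events continuously to 30 days after the last dose. Bedside assessment and adverse-event collection are therefore largely covered. The gap is routine hematology and chemistry in a patient with no known toxicity. Many sites may well test before dosing anyway.

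**Conclusion.** The mismatch is real and is written into the schedule; it is not a missing detail. Its size depends on two assumptions. With a common start and nominal visit dates, 7 of 12 maintenance infusions lack a same-month scheduled blood test and 5 of 12 lack one within the preceding month. If the tests move with the CT window, a 28-day look-back can also leave 5 of 12. The last scheduled count can be 2 months old on a common start and 3 months old with a one-month offset.

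A reader might go on to infer that toxicities will be missed in some number, or that the trial's main results are compromised. The documents give no maintenance-phase rate of cytopenia or transaminase elevation, so no number of affected events can be derived. The primary endpoint is assessed at EOI and the toxicity stopping rule covers induction, so neither is touched. This is an inexpensive safety improvement that should be made. It is not an error in the efficacy design.

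**What to change.** Amend section 15.5, the maintenance column of the 15.9 table and footnote g to require hematology and chemistry before each two-monthly maintenance infusion, with results available within a window the sponsor sets (induction uses 24 hours). Leave the CT calendar and the tests at CT visits as they are.

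The cost is a schedule amendment, the matching eCRF entries and about 7 extra routine blood samples per patient who completes maintenance, on days the patient already attends. At the design response rates of 55% and 75%, 43 x 0.55 = 23.7 and 43 x 0.75 = 32.3, or about 24 to 32 patients would enter maintenance. If all of them completed it, the total would be 24 x 7 = 168 to 32 x 7 = 224 samples.
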